9.5 Data Collection and Quality Assurance

Data are collected on electronic case report forms using the Medrio electronic data capture system and database. Qualified monitors review the data electronically and through site monitoring visits to assure that the investigator and staff are compliant with the protocol and applicable regulatory requirements in addition to assuring timely and accurate data collection.

9.6 Statistical Software

SAS 9.4 (SAS Institute, Cary, NC) will be used to create datasets from SAS data exports from the Medrio system for reporting and analysis. Analyses will be performed using SAS 9.4 (SAS Institute, Cary, NC) and SigmaPlot 14.0 (Systat Software, Inc., San Jose, CA).

9.7 Demographics and Baseline Characteristics

Demography and baseline characteristics will be summarized using frequencies and percentages for categorical factors and mean, standard deviation, minimum and maximum, median, and interquartile range for continuous factors.

9.8 Outcome Measures Analyses

Data collected at postprocedure evaluation time points conducted after a participant received additional ENT procedures outside of the study protocol will be excluded

Statistical Analysis Plan TP900 (AERWAY)

from analysis of efficacy outcomes measures as these additional procedures would likely confound the effect of the original Vivaer treatment. For example, a participant who received a septoplasty after the 12-month evaluation will have any efficacy outcome measures that were collected after the septoplasty (24 months and 36 months) excluded from the analysis. Results after receiving additional treatments may be summarized separately.

Nasal Assessment - The visual physical and endoscopic assessment factors summarized to include frequency and percentage of responses in each category for each component of the nasal assessment at baseline, just prior to procedure, immediately after procedure, and 3 months after the procedure.

NOSE Scale score - Categorical responses and scores on the NOSE Scale and its individual components will be subject to multiple summary methods and analyses including the:

- Mean and mean change from baseline at the 3-, 6-, 12-, 24-, and 36-month follow-up evaluations.
- Distribution of NOSE Scale score severity categories (mild, moderate, severe, extreme) at the 3-, 6-, 12-, 24-, and 36-month follow-up evaluations displayed as number and percent.
- Mean, change from baseline in mean, and response distribution of the 5 components of the NOSE Scale score (nasal congestion, nasal blockage, trouble breathing, trouble sleeping, and getting enough air during exercise) at the 3-, 6-, 12-, 24-, and 36-month follow-up evaluations.
- Proportion (%) of responders based on improvement in NOSE Scale score at the 3-, 6-, 12-, 24-, and 36-month follow-up evaluations be displayed as number and percent.

VAS for pain - Summary will include mean (median) VAS pain scores assessed postprocedure and at 3 months.

Participant QoL Questionnaire – Responses to questionnaire items will be summarized by response category (frequency and percent) and by mean (median) response where appropriate at the 3-, 6-, 12-, 24-, and 36-month follow-up evaluations.

Medications - Medications associated with relief or treatment of NAO symptoms or associated with the treatment of adverse events will be documented at baseline and updated as necessary at each evaluation or adverse event. Medications relevant to nasal obstruction may be categorized (eg, antihistamine, intranasal steroid, decongestant, anticholinergic, immunotherapy) for summarization and reporting purposes.

Change in medication use for nasal obstruction symptoms - Proportions of participants reporting increase, decrease, or no change in use for medication

Statistical Analysis Plan TP900 (AERWAY)

categories will be summarized at the 3-, 6-, 12-, 24-, and 36-month follow-up evaluations.

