9.4 PHASE 4: SUBJECT FOLLOW-UP QUESTIONNAIRES AT 6, 12, 24 and 36 MONTHS

Subjects will be contacted for follow-up data collection at **6, 12, 24 and 36 months** calculated from the treatment date.

Study subjects will be asked to complete the following self-reported questionnaires:

- NOSE Score
- Quality of Life (QOL) Questionnaire

If any changes in medication, health status or subject received another nasal procedure, the subject will be instructed to contact the study staff.

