8.2 NOSE Scale Score

To evaluate the significance of a patient's nasal obstruction both before and after the procedure, this study used the well-known patient-reported NOSE Scale for determining the primary assessment of treatment effectiveness. The NOSE Scale is a validated disease-specific health status instrument used by clinicians to measure the outcome of patients treated for nasal obstruction.¹ The NOSE Scale consists of 5 items, each scored using a 5-point Likert scale to make a total score range of 0 through 100, where higher scores indicate worse obstruction. Severity of symptoms can be classified as mild (range, 5-25), moderate (range, 30-50), severe (range, 55-

Statistical Analysis Plan TP900 (AERWAY)

75), or extreme (range, 80-100) nasal obstruction, based on responses to the NOSE survey.²

Treatment responder based on NOSE Scale improvement

Individual participant success (responder) is defined as at least 1 NOSE Scale class improvement, (eg, going from a score in the severe range (55-75) at baseline to a score in the moderate range (30-50) at the follow-up evaluation), or an improvement (decrease) in NOSE Scale score of 20% or more from baseline to the follow-up time point. Other levels of success (definitions of responder) may also be explored.

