8.4 Participant Quality of Life Assessment

The QoL questionnaire consists of 4 parts (Appendix A). The first part has 24 items and asks the participant to rate how much of a problem various symptoms and potential effects of their nasal obstruction present to their quality of life at the time of taking the survey relative to the time prior to having the Vivaer procedure. A 6-point ordered rating scale is used with descriptors:

- No Problem (0)
- Very Mild Problem (1)
- Mild or Slight Problem (2)
- Moderate Problem (3)
- Severe Problem (4)
- Problem as bad as it can be (5).

The second part has 3 questions related to frequency of use of medical products for nasal obstruction symptom relief now compared to before the procedure. Responses are on a 5-point ordered rating scale with descriptors:

- Much less frequently
- Less frequently
- About the same
- More frequently
- Much more frequently.

There is also a response of not applicable if a product was not being used prior to the procedure.

Statistical Analysis Plan TP900 (AERWAY)

The third part has 3 questions. The first is a rating on a 10-point scale of satisfaction with symptom relief following the procedure where 1 represents symptoms have no effect on daily activity and 10 being symptoms completely prevent daily activity. The second question asks if the procedure would be recommended to a friend with similar symptoms (yes or no) and the third question asks if symptoms returned would you undergo the procedure again (yes/no).

The fourth section requests information on general health, including undergoing additional nasal surgery, significant changes in health, and changes to medication regimen.

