9.2 General Considerations and Statistical Methods

Summary descriptive statistics, including mean, median, standard deviation, minimum, maximum, and interquartile range for continuous measures, and frequencies and percentages for categorical outcomes will be presented for all variables of interest. Outcome measures will be presented by time. Confidence intervals will be included for means and medians where appropriate for the various outcome measures.

Informational and exploratory outcomes analyses will use $P < .05$ as a measure of statistical significance. Where feasible, longitudinal analyses of individual outcome

Statistical Analysis Plan TP900 (AERWAY)

measures will incorporate *P*-value adjustment for comparisons of multiple time points. No adjustments will be made due to analyzing multiple outcome measures.

Analyses using repeated measures linear mixed models with multiple comparisons of time points are anticipated for outcome measures conventionally considered continuous data (NOSE). Components of the NOSE Scale score have also been treated as continuous but may also be analyzed using generalized linear models as outcomes represented by ordered categories.

Results will be presented using least square (adjusted) means where data are not complete across all time points.

Nonparametric analysis will be employed where gross violations of assumptions for parametric analyses are demonstrated.

Correlation analysis and regression modeling may be employed for exploratory analyses of relationships between and among various participant demographic and history characteristics and outcome measures, particularly NOSE Scale scores and components.

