9.4 Missing Values

Outcome measures will be analyzed by using available data only. No imputations are anticipated unless part of a subgroup analysis of interest.

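### Participants who have a further ENT procedure drop out of the later responder and NOSE severity percentages, and no planned analysis counts a further obstruction procedure as non-response

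*SAP*

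**What the plan says.** SAP 9.8 sets the rule: "Data collected at postprocedure evaluation time points conducted after a participant received additional ENT procedures outside of the study protocol will be excluded" "from analysis of efficacy outcomes measures as these additional procedures would likely confound the effect of the original Vivaer treatment". Its worked example is a septoplasty after the 12-month evaluation, which removes that participant's 24- and 36-month efficacy data. Data from before the procedure are kept. What happens to the later data is left open: "Results after receiving additional treatments may be summarized separately".

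SAP 9.4 covers missing values: "Outcome measures will be analyzed by using available data only. No imputations are anticipated unless part of a subgroup analysis of interest".

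SAP 8.2 defines response from NOSE alone: "Individual participant success (responder) is defined as at least 1 NOSE Scale class improvement", or a fall of at least 20% from baseline. A further procedure is not part of the definition. Other responder definitions are allowed but not specified.

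SAP 9.8 reports responders and severity categories as number and percent at 3, 6, 12, 24 and 36 months. It does not name the analysis set that forms the denominator and does not ask for the number excluded at each visit.

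SAP 9.2 plans a model for the continuous score: "Analyses using repeated measures linear mixed models with multiple comparisons of time points are anticipated for outcome measures conventionally considered continuous data (NOSE").

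Information on further surgery is requested. SAP 8.4 describes the questionnaire: "The fourth section requests information on general health, including undergoing additional nasal surgery". Protocol 9.4 adds: "If any changes in medication, health status or subject received another nasal procedure, the subject will be instructed to contact the study staff".

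**The concern.** A further procedure for nasal obstruction after the study treatment is itself information about how long the benefit lasted. Under SAP 9.8 and 9.4 it is handled like a missed questionnaire: the participant is no longer counted, either as a success or as a failure. Those who stay in the later percentages are the ones who had no further procedure.

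The SAP's own example is relevant to obstruction. Protocol 2.1 lists severe septal deviation among the common causes, and Protocol 3.3 describes NOSE as an outcome measure after septoplasty. Exclusion criterion 3 (Protocol 8.4) addresses only anatomy needing an adjunctive procedure on the same day or 3 months after treatment, so later procedures are foreseeable.

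The 24- and 36-month percentages are what a reader will use to judge durability, and SAP 2 says results may go into regulatory submissions and manuscripts. As planned, the reader would not know how many participants had been removed or what the rate would be if they were counted. The planned subgroup responder proportions and the description of nonresponders in SAP 9.9 would lose the same people at later visits.

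**Working it through.** **Reading the rule.** The plan gives no figure to reproduce: there is no power calculation, no expected responder rate and no expected rate of further procedures. The first check is therefore on the text.

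- SAP 9.8 removes the data, SAP 9.4 analyses what is available, and imputation is anticipated only within subgroup analyses. The natural reading is that the participant leaves both numerator and denominator.
- SAP 8.2 does not bring the participant back as a non-responder.
- The mixed model in SAP 9.2 concerns the continuous score and does not restore anyone to the percentages.
- The separate summary (SAP 9.8) and other responder definitions (SAP 8.2) are optional. Neither commits to counting the event.

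**Inputs for the illustration.** The planned enrolment of up to 125 comes from SAP 5. The rest are assumptions: a reported responder rate R of 90%, k = 5, 10 or 15 participants with a further obstruction procedure before the visit, and either nobody else or 25 others missing. For orientation, the earlier follow-up study in Protocol 5.0 reported 87% at 18 months and 97% at 24 months, but with a different definition (at least 15 points).

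**(a) Gap between the two rates.** Let N be the participants analysed plus those excluded for a further procedure. The responders number R × (N − k), so

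rate counting procedures as non-response = R × (N − k) / N, and the gap is R × k / N.

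| N | k | Calculation | Rate |
|---|---|---|---|
| 125 | 1 | 0.90 × 124/125 | 89.3% |
| 125 | 5 | 0.90 × 120/125 | 86.4% |
| 125 | 10 | 0.90 × 115/125 | 82.8% |
| 125 | 15 | 0.90 × 110/125 | 79.2% |
| 100 | 5 | 0.90 × 95/100 | 85.5% |
| 100 | 10 | 0.90 × 90/100 | 81.0% |
| 100 | 15 | 0.90 × 85/100 | 76.5% |

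The rows with N = 100 have 25 others missing at that visit. The choice of R matters little: at k = 10 of 125 the gap is 0.87 × 0.08 = 7.0 points for R = 87% and 0.97 × 0.08 = 7.8 points for R = 97%.

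**(b) Bias against the result had nobody had a further procedure.** This is a different target. With e = k/125, the target is (1 − e) × p_stay + e × p_excl, where p_excl is the response rate the excluded participants would have had without the procedure. The planned analysis reports p_stay, so

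bias = e × (p_stay − p_excl).

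With p_stay = 90%, in percentage points:

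| p_excl | e = 4% | e = 8% | e = 12% |
|---|---|---|---|
| 0% | +3.6 | +7.2 | +10.8 |
| 50% | +1.6 | +3.2 | +4.8 |
| 90% | 0 | 0 | 0 |
| 100% | −0.4 | −0.8 | −1.2 |

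The gap in (a) is above zero whenever at least one such procedure occurs and the reported rate is not zero. The bias in (b) is upward only if the excluded participants would have responded less often than those kept.

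**The case against.** The strongest reply is that this is a prespecified and explained choice of estimand, not an error. The rule prevents the benefit of a later septoplasty from being credited to the study device, and it keeps earlier data. A rate that adds people as failures must be lower than one that leaves them out, so the gap in (a) compares two quantities and does not prove bias. For bias proper, even the direction is not established. The procedure rate is unknown, no test or threshold depends on the result, and with exclusion counts a reader could work out the second responder rate unaided.

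Much of that stands. The exclusion analysis should stay, the figures are illustrations, and removal from the denominator is inferred, because SAP 9.8 does not state it. But the SAP does not require the exclusion counts, does not state the denominator and does not say that its percentages describe only participants without a further procedure. The counts alone would also not separate obstruction procedures from other ENT procedures.

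A second reply is that some later surgery will address a coexisting cause of obstruction, in someone who may still meet the NOSE criterion, and that its purpose would be judged without blinding. This is a fair limit on the second rate, which is deliberately strict. Such surgery is still further treatment for the symptom the study targets, and the strict rate would sit beside the planned one, not replace it.

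**Conclusion.** The concern holds and should be fixed. Followed as written, SAP 9.8 and 9.4 give later responder and severity percentages that omit participants who needed a further procedure for obstruction, and no committed analysis counts them.

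Under the assumed 90% rate, the difference from counting them as non-responders runs from 0.7 points (one of 125) to 10.8 points (15 of 125), or 13.5 points with 15 of 100. Bias against a no-further-procedure target ranges from −1.2 to +10.8 points in the scenarios shown and cannot be signed from the documents. All of this rests on assumed procedure and response rates and on the natural reading of the denominator. The point affects how durability is described; it overturns no formal conclusion, because the study has no hypothesis test.

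**What to change.** Amend SAP 9.8 as follows.

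1. At each visit, add an FAS responder rate in which a participant with an additional procedure for nasal obstruction stays in the denominator as a non-responder from that procedure on. State its denominator. Show it beside the present analysis, and label the latter as the result without further procedure. Give these participants their own row in the severity table.
2. Limit the non-response rule to procedures aimed at nasal obstruction, classified from the reported procedure, with a brief record check where the purpose is unclear.
3. Report the number excluded at each visit, and make the separate summary of results after additional treatment a commitment instead of an option.

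The cost is SAP wording, one responder line and one severity row per visit. Further surgery is already asked about, but the documents do not say that its purpose is recorded, so some classification work is needed. If any such procedure occurs, the second responder rate will be less favourable than the first. No new visits or participants are required.

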Aerin Medical conducted a prospective, non-randomized, multicenter 26-week trial in September 2016 at 8 study centers in the United States with the primary objective to evaluate safety and efficacy of the Vivaer[®] ARC Stylus for treating the nasal valve area to improve the symptoms in those diagnosed with nasal airway breathing. Fifty subjects participated in the study. Subjects exhibited significant symptoms of nasal obstruction attributed to internal nasal valve dysfunction. The nasal valve was determined to be the primary or significant contributor to subjects' nasal obstruction based on clinical presentation, physical examination, and nasal endoscopy. Subjects were required to have a nasal obstruction symptom evaluation (NOSE) score ≥ 60 to be included in the study.

The Vivaer[®] ARC Stylus was used to apply lateral pressure to a weakened ULC, repositioning the tissue while heating it and thereby widening the nasal airway (see Figure 5). Contraction of the treated area during the healing process would serve to curve the treated portion of the ULC, creating a wider nasal airway and a stiffer nasal valve wall (Figure 6).

[figure not shown]

Figure 4. Obstructed Nasal Valve

[figure not shown]

Figure 5. Vivaer[®] repositioning and treating ULC

[figure not shown]

Figure 6. Contraction of ULC (left) and Healed ULC (right)

Of the 50 subjects enrolled in the study, 49 underwent the procedure on both nostrils and 1 subject had the procedure on one nostril only. Forty-nine subjects were available for the primary analysis at the 26-week evaluation. One subject was unavailable for the 26-week evaluation

Safety was evaluated by nasal status assessment, including both a physical assessment and an endoscopic visual assessment of the target nasal valve area within each nostril was done at baseline, immediately prior to and after the procedure, and at each subsequent follow-up visit. Other safety measures were a post procedure pain assessment using a visual analog scale (VAS) and monitoring of medications.

There were no deaths in the study. There were 36 adverse events reported from 20 subjects. None of the events were considered related to the device, although 13 were considered related to the procedure. Most events occurred in the period from the procedure to 4 weeks. Two serious adverse events were reported from 2 subjects. Neither was related to the device or procedure. There were no unanticipated adverse events and no adverse device effects.

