4 STUDY OBJECTIVES AND ENDPOINTS

The primary objective of this study is to continue to evaluate the effectiveness of the Vivaer ARC Stylus for treating the nasal valve area to improve symptoms in those diagnosed with NAO. Effectiveness is assessed through several outcome measures and endpoints as described in Table 1. Outcome measures are further described in Section 8.

Statistical Analysis Plan TP900 (AERWAY)

Table 1. Objectives and endpoints.

Objective	Outcome measures and Endpoints
Evaluate effectiveness through symptom improvement.	
Nasal Obstruction Symptom Evaluation (NOSE) Scale score:
 
 • Mean and mean change from baseline at the 3-, 6-, 12-, 24-, and 36-month follow-up evaluations. • Distribution of NOSE Scale score severity categories (mild, moderate, severe, extreme) at the 3-, 6-, 12-, 24-, and 36-month follow-up evaluations. • Mean, change from baseline in mean, and response distribution of the 5 components of the NOSE Scale score (nasal congestion, nasal blockage, trouble breathing, trouble sleeping, and getting enough air during exercise) at the 3-, 6-, 12-, 24-, and 36-month follow-up evaluations. • Proportion of responders based on improvement in NOSE Scale score at the 3-, 6-, 12-, 24-, and 36-month follow-up evaluations.
Evaluate effectiveness through participant quality of life (QoL) questionnaire feedback.	
QoL questionnaire
 
 • Item response distributions and means where appropriate, at the 3-, 6-, 12-, 24-, and 36-month follow-up evaluations.
Evaluate safety through the safety profile.	
Adverse events
 
 • Frequency of device-related and procedure-related serious adverse events through the 3-month evaluation • Incidence (type, severity, relatedness) of adverse events overall and by follow-up interval.
Evaluate Other Exploratory Outcome Measures	
Nasal Assessment
 
 • Item response distributions prior to the procedure, immediately after the procedure, and at 3 months after the procedure. 
Visual analog scale (VAS) for pain
 
 • VAS pain score assessed at 3 months. 
Medications
 
Updates to current medications or any new or changed medications at the 3-, 6-, 12-, 24-, and 36-month follow-up evaluations.

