5 SAMPLE SIZE

The study was designed to enroll up to 125 participants at up to 20 sites. This was initially a registry-type study for collection of data from a substantial number of participants receiving the Vivaer procedure representing diverse clinics and geographical areas but was implemented as a postmarket single-arm study. No formal power analysis was performed; however, substantially smaller sample sizes were found to be sufficiently powerful in prior

Statistical Analysis Plan TP900 (AERWAY)

studies to draw clinically and statistically meaningful conclusions regarding efficacy and safety of the procedure. The larger sample size in this postmarket study was used to potentially support exploratory subgroup analyses of interest.

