9.10 Safety Analysis

All adverse events (AE) will be analyzed for all participants. Adverse events are coded using a custom Aerin Medical dictionary so that adverse events may be categorized for analysis at an appropriate level of detail. Listings will be provided to detail individual events. The number of participants, number of AEs, and the proportion of participants reporting each AE will be summarized. Multiple occurrences of the same AE for a participant will be noted but only counted once for reporting of AE incidence. Seriousness and severity of AEs and their relationship to the device and procedure will be summarized. A time course of adverse events will be presented. Any unanticipated adverse device experiences or adverse events that occur at an unexpectedly high incidence rate will receive detailed analyses. Narratives will be presented for all deaths, serious adverse events, unexpected adverse device experiences, and participants withdrawn due to an adverse event.

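### Nasal examination findings are tabulated visit by visit and reach the safety summaries only if also recorded as adverse events, so new or worsened signs cannot be told from resolved ones where a sign can pre-exist

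*SAP*

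**What the plan says.** SAP 8.1 lists the nasal assessment items. Nearly all are possible local effects of the procedure, graded on four levels from absent to severe and examined within each nostril. One item, widening of the nasal valve at 3 months, is a benefit on the same scale.

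SAP Table 1 places the assessment under "Evaluate Other Exploratory Outcome Measures", apart from the safety objective, which lists only adverse events. Its endpoint is "Item response distributions prior to the procedure, immediately after the procedure, and at 3 months after the procedure". SAP 9.8 repeats this as the "frequency and percentage of responses in each category for each component of the nasal assessment" at each time point. There is no shift table, no definition of a new or worsened finding, and no stated unit of summary (nostril or participant).

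SAP 9.10 is confined to adverse events: "The number of participants, number of AEs, and the proportion of participants reporting each AE will be summarized". It does not mention the nasal assessment, and neither document says when a finding becomes an adverse event. In the sponsor's pivotal trial, by contrast, Protocol 5.0 reports that "Safety was evaluated by nasal status assessment, including both a physical assessment and an endoscopic visual assessment".

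**The concern.** The examination is the study's only structured look at the treated tissue. By Protocol Table 1, the 3-month visit is the only scheduled examination after the day of treatment, and SAP 3 has later follow-up done remotely by phone. An endoscopic sign that is not turned into an adverse event at 3 months has no later scheduled examination to catch it.

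The adverse event route leaves room for that. Protocol 9.6 and SAP 8.6 describe asking participants about experiences related to the procedure. A participant may not notice mild crusting or swelling seen through an endoscope, and whether the investigator records it separately is a matter of judgement.

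The descriptive table does not fill the gap for signs that can precede treatment. Pre-existing findings are plausible: Protocol 8.4 excludes nasal surgery other than on the valve only within the preceding three months, and SAP 9.9 expects participants with earlier septoplasty or turbinate surgery and with enlarged turbinates. One participant's resolved sign can then offset another's new one. The SAP plans within-participant change for NOSE and direction of change for medication use, but nothing comparable for local findings.

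**Working it through.** The plan has no figure to reproduce: "No formal power analysis was performed", and no rate or threshold is given for any nasal finding. The check is what two visit percentages can reveal about new onset.

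**Inputs**
- N = 125 participants with both examinations. This is the planned ceiling in SAP 5: "The study was designed to enroll up to 125 participants at up to 20 sites". SAP 9.4 uses available data, so the paired number may be smaller.
- c0 = number with the finding just before the procedure, and c3 = number with it at 3 months. Neither is in the documents. Assumed ranges are 0% to 40% before and 4% to 20% at 3 months.

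**Formula**

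c3 = c0 − resolved + new, so new = (c3 − c0) + resolved. The table gives c0 and c3 but not the number resolved. Hence

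max(0, c3 − c0) ≤ new ≤ min(c3, N − c0).

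**Results (assumed counts, N = 125)**

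| Before | 3 months | Net change (points) | New cases the table allows |
|---|---|---|---|
| 0 (0.0%) | 5 (4.0%) | +4.0 | exactly 5 |
| 2 (1.6%) | 5 (4.0%) | +2.4 | 3 to 5 |
| 5 (4.0%) | 5 (4.0%) | 0.0 | 0 to 5 |
| 12 (9.6%) | 12 (9.6%) | 0.0 | 0 to 12 |
| 25 (20.0%) | 12 (9.6%) | −10.4 | 0 to 12 |
| 25 (20.0%) | 25 (20.0%) | 0.0 | 0 to 25 |
| 50 (40.0%) | 25 (20.0%) | −20.0 | 0 to 25 |

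Take the fifth row. The net change is 12 − 25 = −13, that is −13/125 = −10.4 points. With 13 resolved, new = −13 + 13 = 0. With all 25 resolved, new = −13 + 25 = 12. Both produce the same planned table.

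A paired table separates them. Among the 125 − 25 = 100 participants free of the finding beforehand, the two extremes are 0/100 (95% CI 0% to 3.6%) and 12/100 = 12.0% (6.4% to 20.0%). Over all 125 pairs they are 0/125 (0% to 2.9%) and 12/125 = 9.6% (5.1% to 16.2%). Intervals are Clopper-Pearson.

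**What drives it**
- The number hidden is the smaller of new and resolved, so it cannot exceed the smaller of c0 and c3. With c0 = 0 it is nil (first row).
- The same argument holds at each severity cut, so worsening from mild to moderate or severe can be hidden in the same way.
- Collapsing to the worse nostril recreates the problem within a participant. A mild sign that clears on the left and appears on the right reads as mild at both visits.

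**The case against.** The strongest reply is that local harms do have a route into safety. Protocol 10.1 defines an adverse event broadly, with no need for a link to the device, and requires each to be recorded and judged for relatedness, onset, severity and duration. Protocol 9.3 has adverse events evaluated at the same 3-month visit as the endoscopy. SAP Table 1 and SAP 9.10 then summarise all of them. This stands. A reader might infer that local findings are kept out of the safety profile altogether, and the documents do not support that. What remains is that entry depends on a separate, judgement-based recording step with no stated rule.

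A reader might also infer that numbness or saddle-nose deformity could be masked. Nothing in the documents suggests that either is present before treatment and likely to clear by 3 months. If absent beforehand, its 3-month percentage is already the new-onset rate. Blanching is assessed only after the procedure, and bleeding at injection or treatment sites can hardly precede it.

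Nor is 3 months the only examination after treatment. The area is also inspected immediately after the procedure and SAP 9.8 reports that time point.

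The valve-widening item cannot conceal a harm, because each component is tabulated separately with no pooled score. The awkwardness is one of labelling: a severe grade would be the favourable one.

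Finally, the study is descriptive, SAP 9.8 sets a minimum content, SAP 2 permits further documented analyses, and the pivotal trial's classification does not bind this study. All true, but none of it commits the sponsor to looking at new findings.

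**Conclusion.** The point holds in limited form. New local findings reach the safety summaries only through separate adverse event recording, and the planned nasal assessment table cannot back that up for signs that can pre-exist: redness, swelling, obstruction from oedema, crusting and possibly soreness. For those, new onset and worsening cannot be recovered from the per-visit percentages, although the examinations needed to pair them are already collected.

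The size is unknown, since no prevalence is given. In the illustration, an apparent 10.4-point improvement fits 0 to 12 new cases. Twelve is the upper limit under assumed counts and complete pairs, not an estimate. For items absent before treatment there is no masking. The effectiveness results are untouched. This is a worthwhile and inexpensive improvement to the safety reporting, and does not show that harms have been hidden.

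**What to change.** - **SAP 9.8:** keep the planned distributions, including the immediate post-procedure time point. Add, for each harm item, a per-nostril shift table on paired data with the just-before-procedure examination as reference and 3 months as outcome.
- **SAP 9.10:** on the safety analysis set, report for each harm item the number and percent of participants with a new or worsened finding in either nostril, with a 95% CI and the paired denominator. Classify each nostril first and then combine; do not compare worse-nostril grades.
- **Listing:** show each new or worsened finding beside its adverse event record, or note that none exists.
- **Valve widening:** tabulate this item apart from the harm items.

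The cost is SAP wording plus one table and one listing from data already collected, with no new visits or tests. The safety profile may look less favourable.
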